### 8.3.2 DEFINITION OF SERIOUS ADVERSE EVENTS (SAE)

**REQUIRED TEXT:** Being key informant interviews or focus groups, shared decision making and cost capture practices, we do not anticipate any serious medical, adverse events.

**ADRD & SDOH Supplements:** n/a

### 8.3.3 CLASSIFICATION OF AN ADVERSE EVENT

N/A

#### 8.3.3.1 SEVERITY OF EVENT

**REQUIRED TEXT**

N/A

#### 8.3.3.2 RELATIONSHIP TO STUDY INTERVENTION

**REQUIRED TEXT:** Being key informant interviews or focus groups, shared decision making and cost capture practices, we do not anticipate any serious medical, adverse events.

The clinician's assessment of an AE's relationship to study procedure is part of the documentation process, but it is not a factor in determining what is or is not reported in the study. If there is any doubt as to whether a clinical observation is an AE, the event should be reported. All AEs must have their relationship to the study procedure assessed. To help assess, the following guidelines are used.

- **Related** – The AE is known to occur with the study procedure, there is a reasonable possibility that the study procedure caused the AE, or there is a temporal relationship

between the study procedure and event. Reasonable possibility means that there is evidence to suggest a causal relationship between the study procedure and the AE.

- **Not Related** – There is not a reasonable possibility that the study procedure caused the event, there is no temporal relationship between the study procedure and event onset, or an alternate etiology has been established.

## OR

For all collected AEs, the clinician who examines and evaluates the participant will determine the AE's causality based on temporal relationship and his/her clinical judgment. The degree of certainty about causality will be graded using the categories below.

- **Definitely Related** – There is clear evidence to suggest a causal relationship, and other possible contributing factors can be ruled out.
- **Probably Related** – There is evidence to suggest a causal relationship, and the influence of other factors is unlikely.
- **Possibly Related** – There is some evidence to suggest a causal relationship (e.g., the event occurred within a reasonable time after study procedure). However, other factors may have contributed to the event (e.g., the participant's clinical condition, other concomitant events). Although an AE may rate only as "possibly related" soon after discovery, it can be flagged as requiring more information and later be upgraded to "probably related" or "definitely related", as appropriate.
- **Unlikely to be Related** – A clinical event, whose temporal relationship to study procedure makes a causal relationship improbable (e.g., the event did not occur within a reasonable time after study procedure) and in which other factors provide plausible explanations (e.g., the participant's clinical condition, other concomitant treatments).
- **Not Related** – The AE is completely independent of study procedure, and/ or evidence exists that the event is definitely related to another etiology. There must be an alternative, definitive etiology documented by the clinician.

---

### 8.3.3.3 EXPECTEDNESS

**REQUIRED TEXT:** Being key informant interviews or focus groups, shared decision making and cost capture practices, we do not anticipate any serious medical, adverse events.

The principal investigator will be responsible for determining whether an AE is expected or unexpected. An AE will be considered unexpected if the nature, severity, or frequency of the event is not consistent with the risk information previously described for the study intervention.

---

#### 8.3.4 TIME PERIOD AND FREQUENCY FOR EVENT ASSESSMENT AND FOLLOW-UP

**REQUIRED TEXT:** Being key informant interviews or focus groups, shared decision making and cost capture practices, we do not anticipate any serious medical, adverse events.

The occurrence of an AE or SAE may come to the attention of study personnel during study visits and interviews of a study participant presenting for medical care, or upon review by a study monitor. All AEs including local and systemic reactions not meeting the criteria for SAEs will be captured on the appropriate CRF. Information to be collected includes event description, time of onset, clinician's assessment of severity, (if applicable) relationship to study intervention (assessed only by those with the training and authority to make a diagnosis), and time of resolution/stabilization of the event. All AEs occurring while on study must be documented appropriately. All AEs will be followed to adequate resolution.

Any medical condition that is present at the time that the participant is screened will be considered as baseline and not reported as an AE. However, if the study participant's condition deteriorates at any time during the study, it will be recorded as an AE. UAPs will be recorded in the data collection system throughout the study.

Changes in the severity of an AE will be documented to allow an assessment of the duration of the event at each level of severity to be performed. AEs characterized as intermittent require documentation of onset and duration of each episode.

The PI will record all reportable events with start dates occurring any time after informed consent is obtained until 30 (for non-serious AEs) or until resolution or stabilization (for SAEs) after the last day of study participation. At each study visit, the investigator will inquire about the occurrence of AE/ SAEs since the last visit.

---

#### 8.3.5 ADVERSE EVENT REPORTING

**REQUIRED TEXT:** The investigator must record non-serious adverse events and report to DSMC and IRB according to timetable for reporting specified in section 10.1.6.

---

#### 8.3.6 SERIOUS ADVERSE EVENT REPORTING

**REQUIRED TEXT:** The investigator must record all serious adverse events and report to DSMC and IRB according to timetable for reporting specified in section 10.1.6.

- Other SAEs will be submitted to the National Cancer Institute within 72 hours of site awareness.

---

### 8.3.7 EVENTS OF SPECIAL INTEREST

N/A

---

### 8.3.8 REPORTING OF PREGNANCY

N/A

## 8.4 UNANTICIPATED PROBLEMS

---

### 8.4.1 DEFINITION OF UNANTICIPATED PROBLEMS (UAP)

#### **REQUIRED TEXT FOR SINGLE-SITE STUDIES:**

This study will use the COMIRB definition of UAP. An unanticipated problem is any event or information that was unforeseen and indicates that the research procedures caused harm (including physical, psychological, economic, or social harm) to participants or others or indicates that participants or others are at increased risk of harm than was previously known or recognized.

---

### 8.4.2 REPORTING OF UNANTICIPATED PROBLEMS

#### **REQUIRED TEXT FOR SINGLE-SITE STUDIES:**

This study will follow COMIRB's guidance for UAP reporting and the DSMC's requirements (discussed below). AEs, noncompliance and protocol violations will be recorded and reported as required either promptly (within 5 days of Sponsor-Investigator's knowledge) or at the time of the study's continuing review.

It is the responsibility of the PI to report incidents or events that meet the criteria for UAPs reporting to their IRB using the IRB's standard UAP form. The PI is responsible for reporting the UAP to the UCCC DSMC.

## 9 STATISTICAL CONSIDERATIONS

### 9.1 STATISTICAL HYPOTHESES

*Reach:* We will assess the percentage of eligible patients that receive one or more elements of the intervention. Representativeness will be assessed by comparing participants to those who opt out on available demographic and clinical indicators (e.g., age, gender, comorbidities) from chart review.

*Effectiveness:* We will assess the measures at the time points indicated in Table 3. Patients will be consented and provided a small incentive to answer surveys about their experiences. The primary outcomes will be:

- *SDM rates:* We will use single item measures of decision predisposition, choice, and enactment. We will also perform EHR/chart review as appropriate to each setting to document receipt of SDM.
- *Decision quality:* Decision quality is defined as “the extent to which the implemented decision reflects the considered preferences of a well-informed patient.” It consists of two domains: knowledge and values. Knowledge will be measured using a measure validated by [name] and team. Value-treatment concordance will be measured using the values-clarity sub-scale of decision conflict. Across all projects and for all measures, we will use versions validated in Spanish, and when not available, the scales will be translated into Spanish, back translated and tested for cultural appropriateness by our Cancer Center Outreach staff.
- *Receipt of smoking cessation advice/counseling/referral:* We will obtain information from both EHR extracts or chart reviews and patient surveys.

Additionally, we will collect the following secondary outcomes:

- *IPDAS process measures:* We will use six questions based on key domains of decision process as outlined in the IPDAS background document. [name] used these questions and found they had high internal consistency (Cronbach’s alpha of 0.78).
- *The Decision Conflict Scale (DCS):* DCS assesses decisional uncertainty. DCS reliability measures include test-retest correlation and Cronbach’s alpha coefficients exceeding 0.78-0.90. It discriminates between groups who make and delay decisions.
- *Understandability and acceptability:* will be measured using the Ottawa Acceptability Scale (OAS). The OAS consists of 8 questions on a 5-point Likert scale.

Patient characteristics data we collect will include basic demographics (age, gender, educational level, health insurance status, employment), and other pertinent medical history, as well as health literacy and subjective numeracy. We will also have data on practice characteristics to provide qualitative contextual information. These data will allow us to report the representativeness of patients who receive this intervention.

*Adoption:* RE-AIM defines adoption as the absolute number, proportion, and representativeness of a) settings and b) staff who are willing to initiate a program. We will measure adoption by the

number of clinics participating (3) divided by the number we invite, and similarly the number of staff who participate vs. those invited. We will also describe the representativeness of participating clinics, compared to other SNOCAP rural primary care clinics, and complete the Expanded CONSORT figure to transparently report on generalizability.

*Implementation:* RE-AIM defines implementation as the extent to which the intervention is implemented as intended. Consistency of PtDA delivery will be assessed across SNOCAP clinics, patient subgroups, and time via surveys, EHR data and chart reviews. Additionally, we assess organizational factors associated with variation in implementation. Key informant interviews will be conducted at baseline and after implementation of the intervention with the clinic director and other staff involved. The goals of these interviews are to identify issues related to implementation/adaptation using procedures of Hall et al (2017) and Rabin et al (2018) and to explore strategies that may be useful in the refinement of subsequent roll-outs and future dissemination. Patients will complete a survey evaluating if and how the patients used the PtDAs with their clinicians. Finally, we will evaluate costs of the intervention and the implementation strategies using the time driven activity-based costing methods used by Drs. [name] and colleagues adapted as described in the Methods Unit below.

*Maintenance:* This will be assessed primarily by exploring whether each of the 3 clinics decides to continue; drop, or adapt/modify using the PtDAs and smoking cessation actions at the end of the study.

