## 5.5 STRATEGIES FOR RECRUITMENT AND RETENTION

**Phase 1.** Practices within the SNOCAP practice based research network have agreed to partner in University of Colorado programs of research by their involvement in the PBRN.

Practice personnel and patients will be approached in person, via phone, or email to enroll them in the program.

We will conduct key informant interviews until we reach saturation for each group and anticipate completing up to 180 interviews (7-8 per group) or until we reach saturation. (Up to 60 interviews per project)

**Phase 2.** Practice staff and care managers will be asked to assist in recruitment by identifying eligible patients under their care that meet the requirements for LCS. This will be done using screening for eligibility criteria from their EHR. We will recruit a minimum of 9 patients and maximum of 12 patients per practice during each of the four 2-month time blocks for survey completion for a total to not exceed 216 patients across 4 practices. Potential participants will be informed and consented by network/research staff.

Practices will be asked to assist in recruitment by identifying eligible patients through review of the EHR, and follow-up with PBRN research staff.

- Option 1: PBRN research staff works with clinic scheduler to strategically identify eligible patients who have upcoming appointments. A list of appointment dates of eligible patients is provided to PBRN research staff including gender, age, smoking status and smoking history (as described in patient eligibility criteria) and contact information.
- Option 2: PBRN research staff mail out letters to eligible patients offering them an opportunity to reach out to us if interested to learn more about the study during their next visit, or a phone call.
- Option 3: When conducting reminder calls, clinic staff offer patients the opportunity to participate. Nurses will then share a list of patients who showed interest for PBRN research staff to reach out.
- Option 4: PBRN research staff traditionally recruit in the waiting room using a flyer or other tool. In past experience, however, this has not been the most efficient strategy given current pandemic restrictions.

A maximum of three (3) attempts will be made to contact participants if non-responsive after recruitment (i.e. phone, email).

ADRD Supplement

- Post flyer in community-based setting where allowed by the organization.

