## 6 STUDY INTERVENTION

### 6.1 STUDY INTERVENTION(S) ADMINISTRATION

(The intervention component is only within Projects #1 & 2)

The study intervention will begin toward the end of our year one activities and after its formative development in phases 1 and 2.

We will follow a multi-faceted implementation strategy that our team has used on similar studies, including:

- *Basic clinician education*: All clinics will receive education on: 1) lung CA screening; 2) SDM, and 3) innovative smoking cessation strategies that integrate with busy primary care workflows.
- *Fidelity to core intervention elements and adaptation to local context*: Our study will achieve an appropriate balance between fidelity and local adaptation. We will emphasize fidelity to core components of the interventions (e.g., PtDA delivered before or during an encounter; delivered by staff or providers at the clinic) and produce both a study protocol made available through clinicaltrials.gov and an implementation and adaptation guide. We will consult on and document adaptation to local settings as necessary for successful implementation using procedures validated by Rabin et al.
- *Centralized patient identification*: Eligible patients will be identified through a central procedure at each site, utilizing site-based EHR system reports, and eliminating reliance on the clinician. As noted above, we will use the approaches of the Moonshot-funded cessation smoking C3I to obtain accurate smoking history data, as well as the extensive experience of Drs. [name] and [name] with EHRs and patient registries.
- *Audit and feedback*: Sites, clinics, and individual clinicians will receive audits and feedback on their LCS services, including SDM and smoking cessation efforts. Information on use of the PtDA, delivery of smoking cessation advice and counseling/referral (most likely to be to the state Quit line) will come from either EHR or chart review of eligible patients as appropriate to each setting. Reports will be produced and disseminated monthly during the

intervention phases. Audits may be conducted in the form of pre/post surveys, direct observation, and/or brief interview about progress (if in-person observation is not allowed).

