## 7.3 LOST TO FOLLOW-UP

There will be 3 attempts to contact participants, after which time they will be excluded from the study.

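### Representativeness for Reach is judged only against patients who opt out, although Reach is a percentage of all eligible patients

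*Combined protocol and SAP*

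**What the plan says.** The Reach paragraph of section 9.1 (Statistical Hypotheses) makes two statements. The first sets the measure: "We will assess the percentage of eligible patients that receive one or more elements of the intervention". The second sets the check on who those patients are: "Representativeness will be assessed by comparing participants to those who opt out on available demographic and clinical indicators", taken from chart review, with age, gender and comorbidities as examples. The plan defines neither participant nor opting out.

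Section 5.5 (Strategies for Recruitment and Retention, Phase 2) gives four ways of recruiting patients for the surveys. In Option 2, "PBRN research staff mail out letters to eligible patients offering them an opportunity to reach out to us if interested". In Option 3, clinic staff offer participation during reminder calls, and then "Nurses will then share a list of patients who showed interest for PBRN research staff to reach out". Option 1 gives research staff a list of eligible patients with appointments, carrying gender, age, smoking status and smoking history. Option 4 is a waiting-room approach.

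Section 6.1 plans a wider frame for the intervention itself: "Eligible patients will be identified through a central procedure at each site, utilizing site-based EHR system reports". Use of the decision aid is to be tracked from the EHR or from chart review of eligible patients.

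Later in section 9.1, after a list of patient characteristics, the plan adds: "These data will allow us to report the representativeness of patients who receive this intervention". No comparator is named there. An Expanded CONSORT figure is promised under Adoption.

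**The concern.** The two statements on Reach use different reference populations. The percentage is over everyone eligible, while the check on representativeness uses only those who opt out. Someone who opts out in the ordinary sense received an offer and answered it, as a participant did. Someone who never replied to a letter, or whose name never passed to the research team, did not. If the second kind of patient differs from the first, a comparison limited to opt-outs does not describe the gap between those reached and those eligible.

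What is at stake is the generalizability statement. The primary endpoint for Project 1 in the synopsis is the best implementation process and the feasibility of a national trial in rural practices, and knowing whom the program reached is part of that. The plan takes the wider view for Adoption, where participating staff are set against those invited and participating clinics against other rural clinics in the network. Only patients get the narrower comparator.

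**Working it through.** **No stated figure to reproduce.** The plan gives no number of eligible patients, no response rate and no refusal rate. The check is a reading of the text, followed by an illustration on assumed inputs.

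**Where each kind of eligible patient falls under the wording of section 9.1**

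| Eligible patient | Route | Group in the planned comparison |
|---|---|---|
| Enrolls | any option | participant |
| Declines when asked directly | Options 1, 3, 4 | opt-out; under Option 3 the plan passes on only interested patients, so research staff may not learn of the refusal |
| Does not answer the letter | Option 2 | not assigned |
| Not reached by the reminder call, so not on the list | Option 3 | not assigned |
| Enrolls, then cannot be contacted | section 7.3 | not stated |

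No other section assigns the third and fourth rows. The second representativeness sentence in 9.1 names no comparator. The Expanded CONSORT figure may count non-responders, but a count does not compare their characteristics.

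**How large the missed difference could be.** Let s be the silent share of non-participants, g_o the difference between opt-outs and participants on some characteristic, and g_n the difference between silent patients and participants.

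- Planned comparison: g_o
- Participants against all non-participants: (1 − s) × g_o + s × g_n
- Difference missed: s × (g_n − g_o)

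The error can go either way. To show how a reassuring result could arise, assume that 50% of both participants and opt-outs are current smokers, so g_o = 0 and the planned gap is 0 points. The gap to all non-participants is then s × g_n, in percentage points:

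| s | g_n = 5 | g_n = 10 | g_n = 20 |
|---|---|---|---|
| 20% | 1 | 2 | 4 |
| 40% | 2 | 4 | 8 |
| 60% | 3 | 6 | 12 |
| 80% | 4 | 8 | 16 |

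The same in counts, all assumed: 400 eligible, 200 participants, 40 opt-outs at 50% and 160 silent patients at 65%. All non-participants: (40 × 0.50 + 160 × 0.65)/200 = 0.62, a gap of 12 points that the planned comparison shows as 0. With 100 opt-outs and 100 silent patients: (100 × 0.50 + 100 × 0.65)/200 = 0.575, a gap of 7.5 points.

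Against all eligible patients the gap shrinks by the factor (1 − p), where p is the share taking part. For p between 25% and 50% it runs from 0.50 × 1 = 0.5 points to 0.75 × 16 = 12 points.

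**The case against.** The strongest objection is that survey recruitment and receipt of the intervention are different things. Options 1 to 4 recruit patients to complete surveys, while Reach counts patients who receive some part of the intervention in the clinic. A patient who ignores the letter can still be given the decision aid and count toward Reach. This stands, and it shapes the fix: a table sorted only by survey enrollment would not show whom the intervention reached, so two comparisons are needed.

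A second objection is that opting out is undefined. If the sponsor counts silence as opting out, the gap closes on paper. That is possible, but it is not the ordinary meaning, and the term would still have to be defined.

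A reader might infer that the three-attempt rule also removes non-responders from view. The documents do not support that. Section 5.5 applies the limit to people who stop responding after recruitment, and section 7.3, headed as loss to follow-up, says "There will be 3 attempts to contact participants, after which time they will be excluded from the study". These people have already been recruited. Nothing says that their chart data leave the participant group, and section 7.2 asks for every effort to obtain information on those who withdraw. What remains is only that the plan does not say in which row they are reported.

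A reader might also infer that most non-participation will be passive. Only Option 2 is clearly passive. Options 1 and 4 allow direct approach, a patient who says no on an Option 3 reminder call has opted out, and no section says how often each option will be used.

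Finally, the illustration sets opt-outs equal to participants, which fixes the planned gap at 0. It shows that the comparison can mislead, not that it will.

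**Conclusion.** The point holds as a cheap improvement. Section 9.1 names a selective comparator for representativeness beside a Reach percentage defined over all eligible patients, and Options 2 and 3 allow eligible patients to fall outside that comparator. The conclusion rests on reading opting out in its ordinary sense.

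The size cannot be derived from the documents. The 1 to 16 points against all non-participants rest on three assumptions: opt-outs identical to participants, a silent share of 20% to 80%, and silent patients differing by 5 to 20 points. The 0.5 to 12 points against all eligible patients add a fourth, that 25% to 50% take part.

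The effect is confined to one descriptive implementation measure in a feasibility pilot. The Reach percentage already has the right denominator, and no effectiveness outcome, power figure or hypothesis test changes.

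**What to change.** In section 9.1, under Reach, replace the single comparison with two:

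- **Intervention reach:** eligible patients who received one or more elements of the intervention against all other eligible patients.
- **Survey participation:** survey participants against all eligible patients, with active opt-outs and non-responders shown separately. Keep recruited patients later lost to follow-up under section 7.3 in the participant group, as a separate row.

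Define participant, opt-out and non-responder in the same place. Use age, gender and the clinical indicators already planned from the EHR or chart review. Add smoking status and smoking history where the site list carries them; the plan specifies those fields only for Option 1.

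The cost is protocol wording, one more descriptive table, and IRB confirmation that non-responders may be summarized in aggregate. The Reach percentage already needs a count of eligible patients at each clinic, so the frame is largely required anyway. The table may be incomplete in places: section 8.2.1 says patient identification will depend on clinic resources, with other means where EHR abstraction is not available. Report any such clinic as incomplete.

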## 4 STUDY DESIGN

### 4.1 OVERALL DESIGN

Our pilot test of shared decision-making and smoking cessation guidelines for LCS will provide a practical test of our initial methods project to refine, develop and validate methods to measure both cost and benefit components of value from multiple stakeholder perspectives. First, though, in this initial pilot, we will refine the pragmatic implementation and replication cost measurement tools our team has already developed, and use these tools in the LCS pilot. *A necessary first step is understanding what costs and outcomes are important to different stakeholders and we will develop and test methods to assess preferences of patients, providers and staff across multiple RE-AIM outcomes in the LCS pilot.* A cost capture template will be piloted and refined during the local implementation of the PtDA. Each project, PtDA for LCS, cost capture template and quantitative/qualitative assessment of value and perspective, will inform our nation dissemination of the PtDA in years 3-5. This will also inform generalizability of the methods and measures developed with respect to other modes of cancer screening.

Our pilot intervention will engage no more than 216 patients using a pragmatic, pre-post design guided by our enhanced RE-AIM/PRISM framework. The primary goal of this intervention is to improve LCS practice by offering a formal SDM process and smoking cessation support aligned with the CMS coverage criteria. We will conduct a type II effectiveness implementation hybrid trial using a pre-post design to evaluate the effectiveness (co-primary outcomes of LCS and decision quality) and implementation at four rural clinics. Space precludes discussion of pragmatic design features, but we have designed this study to be pragmatic using the PRECIS-2 criteria and it scores highly on almost all PRECIS-2 dimensions.

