### 6.1.1 STUDY INTERVENTION DESCRIPTION

Project #1 & 2 within our program of research include an intervention: the PtDA for shared decision making in LCS and cost collection tool.

PtDA: Modification of the LCS PtDA and smoking cessation procedures for rural primary care will occur simultaneously with the phase one key informant interviews. We will review existing PtDAs with stakeholders and develop a modified version for use in rural primary care in collaboration with [name] and colleagues at the University of Michigan who developed an existing LCS tool for use during a primary care encounter using “designing for dissemination” principles. We will follow the stepwise method (see Study Schema) in modifying the SDM content for our LCS pilot.

- *Step 1:* The initial content will be based on a review of existing PtDAs using the International Patient Decision Aid Standards (IPDAS). Testing of [name] LCS PtDA showed significant improvements in knowledge, decision conflict, and improved concordance between patients’ preferences and screening recommendations.
- *Step 2:* Based on existing lung cancer PtDAs, we will draft a low-fidelity paper or digital version allowing for rapid iteration. We will incorporate a host of innovations that we have found facilitate implementation. Our iterative development process follows a user-centered design perspective for the purpose of improving acceptability among end-users, facilitating future implementation. The PtDAs are intended to be used by different end-users, and should be meaningful, helpful and accepted by all. Not only does this provide additional feedback, it creates investment among end users. Additionally, we provide “gist” language to supplement statistics to improve understanding among patients with lower literacy.
- *Step 3:* We will iteratively review a paper-based or digital PtDA with the *multiple stakeholders* engaged in phase one. This review will occur immediately after the qualitative interview.
- *Step 4:* Once modifications are complete, we will draft a high-fidelity, encounter-based version using graphic design resources available at ACCORDS in the Colorado Program for Patient-Centered Decisions.

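### Section 9.1 reports a values-clarity score as value-treatment concordance without comparing it with the decision made, and Sections 4.1 and 9.1 need one primary outcome list with LCS defined

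*Combined protocol and SAP*

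**What the plan says.** Section 9.1, under Effectiveness, lists three primary outcomes: SDM rates, decision quality, and receipt of smoking cessation advice, counseling or referral.

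- Decision quality is defined as "the extent to which the implemented decision reflects the considered preferences of a well-informed patient". The section adds: "It consists of two domains: knowledge and values". Knowledge has its own validated measure. For the other domain: "Value-treatment concordance will be measured using the values-clarity sub-scale of decision conflict".
- For SDM rates: "We will use single item measures of decision predisposition, choice, and enactment". Chart or EHR review of SDM receipt is added.
- The full Decision Conflict Scale (DCS) is a secondary outcome, described thus: "DCS assesses decisional uncertainty".
- On timing: "We will assess the measures at the time points indicated in Table 3". That table is not in the supplied text.

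Section 4.1 says that the pilot will "evaluate the effectiveness (co-primary outcomes of LCS and decision quality) and implementation at four rural clinics". The sentence shortly before it sets the primary goal as better LCS practice through a formal SDM process and cessation support.

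The Section 1.1 synopsis makes implementation processes and the feasibility of a future trial the primary endpoint for Project 1, and improved LCS practice a secondary one. Section 3 gives a further set of primary endpoints: screening infrastructure in rural areas, and stakeholder values and perspectives.

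**The concern.** Concordance, on the plan's own definition, relates two things: what an informed patient prefers and what was decided. The measure assigned to it supplies at most the first. A decision aid that helps patients sort out their values could raise the score while decisions fit those values no more often than before. Followed as written, the plan would report that rise as better concordance within a primary outcome.

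The second problem is which outcomes are primary. A reader of Section 4.1 cannot tell whether the co-primary LCS result concerns delivery of SDM and cessation support or uptake of screening.

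Both matter beyond this pilot. Section 9.2 says that estimates for key outcomes will help to plan the future study, so the label and the unsettled list would carry into that design.

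**Working it through.** No figure in the plan bears on this point. The check sets the passages side by side.

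**A. The concordance label (Section 9.1)**

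1. What the definition needs: (a) the patient's informed preferences, (b) the decision carried out, and (c) a comparison of the two.
2. What is assigned: the values-clarity sub-scale alone. From its name, it measures how clear the patient is about what matters. That is an inference, because the documents cite the scale without giving its items or scoring.
3. Where the decision is recorded: the single items on choice and enactment. These sit under SDM rates, a different primary outcome.
4. Whether (c) exists: no sentence in Section 9.1 links the sub-scale score to those items. Section 9.4.2, headed as the primary efficacy analysis, covers qualitative coding, comparisons of RE-AIM ratings and a Phase 2 power statement that names no outcome. It adds no such step.
5. Result: if the sub-scale measures what its name says, any change in it is compatible with no change in how often decisions match preferences. One of the two decision-quality domains is affected. Knowledge is not.
6. Overlap: the sub-scale is part of the DCS, so the same responses feed a primary outcome as concordance and a secondary one as decisional conflict. Section 9.1 does not mention this.

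**B. The primary outcome lists (Sections 4.1 and 9.1)**

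| Section | Primary effectiveness outcomes | Count |
|---|---|---|
| 4.1 | LCS; decision quality | 2 |
| 9.1 | SDM rates; decision quality; cessation support received | 3 |

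1. If LCS means LCS practice (SDM plus cessation support), the three outcomes in Section 9.1 fit under the two headings in Section 4.1 and the lists align.
2. If LCS means screening uptake, the lists share 1 outcome (decision quality) and together name 2 + 3 - 1 = 4. Section 9.1 then names no primary uptake outcome, although its enactment item might capture one.
3. Section 9.1 does not say which meaning applies. Section 9.4.2 does not say which list governs, and Section 9.4.3 (secondary endpoints) is marked not applicable.

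**The case against.** On the label: Section 9.1 says that decision quality has a values domain, and a values-clarity sub-scale is a natural measure for it. Choice and enactment are collected as well. Using a sub-scale under a primary outcome and the full scale as a secondary is not an error in itself. All of this stands. It supports keeping the sub-scale, but not calling its score concordance.

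On the lists: the stated primary goal in Section 4.1, and the description of LCS services in Section 6.1, make the practice reading plausible, and on that reading the lists agree. Table 3 may also list each measure, including one for LCS. This stands too. The point is that the reader has to supply the reading.

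Three stronger readings are tempting, and the documents do not support them.

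- A reader might infer from Section 6.1.1 that the plan itself separates decision conflict from value-treatment concordance. The concordance reported there is between preferences and screening recommendations, which is a different construct.
- A reader might take the remark on decisional uncertainty as proof of what the sub-scale measures. It describes the full DCS.
- A reader might infer that Section 1.1 contradicts Section 4.1 by ranking improved LCS practice as secondary. The synopsis list covers several Center projects, and its primary endpoint for Project 1 is feasibility. A Center-level feasibility endpoint can coexist with trial-level effectiveness outcomes. What is missing is a statement of how they relate.

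**Conclusion.** The point holds in two limited parts and should be fixed.

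First, the concordance label in Section 9.1 is not supported by any described comparison with the decision. As written, clearer values would be reported as better concordance in one of the two domains of a primary outcome. This rests on the sub-scale measuring what its name says. The missing comparison step is plain from the text and needs no such assumption.

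Second, Sections 4.1 and 9.1 word the primary effectiveness outcomes differently and leave LCS undefined. On the practice reading the difference is only one of wording. On the uptake reading it is substantive: one outcome shared out of four, and no primary uptake outcome in Section 9.1. The documents do not settle which applies, so a flat contradiction is not established. Table 3 is unseen and may supply a measure.

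**What to change.** 1. In Section 9.1, report the sub-scale as values clarity within the values domain. State that it is also part of the secondary DCS.
2. Claim concordance only if patients' stated values or preferences are compared with the decision made. The choice and enactment items already collected supply the decision side. The plan would need to name the values or preference side and the rule for a match.
3. Define LCS in Section 4.1 and use one primary list in Sections 4.1 and 9.1. If uptake is meant, name its measure and time point. Which outcomes are primary is the investigators' choice.
4. State how these trial-level outcomes relate to the Center-level endpoints in Section 1.1 (feasibility primary, improved LCS practice secondary) and to the primary endpoints in Section 3.

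Cost: relabelling and reconciling are wording edits. Keeping concordance requires a defined comparison and possibly a values or preference item; keeping uptake requires a named survey item or chart field. The downside of relabelling alone is that decision quality is then reported as knowledge plus values clarity, with no claim that decisions matched preferences.
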